8.2.2. Adverse Event Summaries

An overall summary of AEs by treatment group will include:

- Number (%) of participants reporting any TEAEs
- Number (%) of participants reporting any ASRs
- Number (%) of participants reporting any serious TEAEs
- Number (%) of participants reporting any Grade 3 or higher TEAEs
- Number (%) of participants reporting any treatment-related TEAEs
- Number (%) of participants who temporarily interrupted study drug because of TEAEs
- Number (%) of participants who permanently discontinued study drug because of TEAEs
- Number (%) of participants who had a fatal TEAE

The following summaries will be produced by MedDRA term (if 2 or fewer participants appear in a table, a listing may be appropriate):

- Summary of TEAEs by SOC and PT
- Summary of TEAEs by PT in decreasing order of frequency
- Summary of TEAEs $\geq 1\%$ in any treatment group by PT in decreasing order of frequency

- Summary of ASRs by PT in decreasing order of frequency
- Summary of exposure-adjusted incidence rates of TEAEs by PT in decreasing order of frequency
- Summary of Grade 3 or higher AEs by SOC and PT
- Summary of Grade 3 or higher AEs by PT in decreasing order of frequency
- Summary of serious TEAEs by SOC and PT
- Summary of serious TEAEs by PT in decreasing order of frequency
- Summary of treatment-related TEAEs by SOC and PT
- Summary of treatment-related TEAEs by PT in decreasing order of frequency
- Summary of Grade 3 or higher treatment-related TEAEs by SOC and PT
- Summary of treatment-related serious TEAEs by SOC and PT
- Summary of TEAEs with a fatal outcome by SOC and PT
- Summary of TEAEs leading to dose interruption of study drug by SOC and PT
- Summary of TEAEs leading to discontinuation of study drug by SOC and PT

8.3. Clinical Laboratory Tests

8.3.1. Laboratory Value Definitions

All laboratory assessments will be performed using a central laboratory except for urine pregnancy tests (as applicable). Laboratory values and change from baseline values will be summarized descriptively by visit, and non-numeric test values will be tabulated when necessary.

The baseline value will be determined using the last nonmissing value collected before the first application, prioritizing scheduled assessments for baseline identification over unscheduled visits. The last record before application in the highest priority will be considered the baseline record. For baseline laboratory candidates with the same date and time in the same priority category, additional rules may be provided after consultation with the medical monitor to delineate which value will be defined as baseline.

8.3.2. Laboratory Value Summaries

Clinical laboratory tests, including hematology and serum chemistry, will be performed at the Protocol-specified visits. If specific safety issues arise, additional unscheduled laboratory tests/analyses may be performed at the discretion of the investigator.

All test results and associated normal ranges from central laboratories will be reported in SI units. All tests with numeric values will have a unique unit per test. Any laboratory test results and associated normal ranges from local laboratories will be converted to SI units.

When there are multiple laboratory nonmissing values for a participant's particular test within a visit window, the laboratory value with the smallest laboratory sequence number will be used in by-visit summaries.

For test results that will be summarized with available normal ranges, the number and percentage of participants with the laboratory values being low (but never high), normal, high (but never low), and both low and high will be calculated for each test. This shift summary will be produced for each test for the safety population in DB and TE periods. Shift tables will also be presented showing change in CTCAE grade from baseline to worst grade postbaseline. The denominator for the percentage calculation will use the number of participants in the baseline category.

8.4. Vital Signs

Values at each scheduled visit, change, and percentage change from baseline for vital signs, including SBP, DBP, pulse, respiratory rate, and body temperature will be summarized descriptively.

Criteria for clinically notable vital sign abnormalities are defined in [Table 5](#), [Table 6](#), and [Table 7](#). The abnormal values for participants exhibiting clinically notable vital sign abnormalities will be listed along with their assigned treatment group. Alert vital signs are defined as an absolute value outside the defined range and percentage change > 25%. The abnormal values for participants exhibiting alert vital sign abnormalities will be listed.

Table 5: Criteria for Clinically Notable Vital Sign Abnormalities for 12 to 15 Years Old

Parameter	High Threshold	Low Threshold
Systolic blood pressure	> 131 mmHg	< 110 mmHg
Diastolic blood pressure	> 83 mmHg	< 64 mmHg
Pulse	> 100 bpm	< 60 bpm
Temperature	> 38.0°C	< 35.5°C
Respiratory rate	> 20 breaths/min	< 8 breaths/min

Table 6: Criteria for Clinically Notable Vital Sign Abnormalities for 16 to 17 Years Old

Parameter	High Threshold	Low Threshold
Systolic blood pressure	> 120 mmHg	< 90 mmHg
Diastolic blood pressure	> 85 mmHg	< 50 mmHg
Pulse	> 100 bpm	< 45 bpm
Temperature	> 38.0°C	< 35.5°C
Respiratory rate	> 20 breaths/min	< 8 breaths/min

Table 7: Criteria for Clinically Notable Vital Sign Abnormalities for ≥ 18 Years Old

Parameter	High Threshold	Low Threshold
Systolic blood pressure	> 155 mmHg	< 85 mmHg
Diastolic blood pressure	> 100 mmHg	< 40 mmHg
Pulse	> 100 bpm	< 45 bpm
Temperature	$> 38^{\circ}\text{C}$	$< 35.5^{\circ}\text{C}$
Respiratory rate	> 20 breaths/min	< 8 breaths/min

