5.1. Inclusion Criteria

Participants are eligible to be included in the study only if all of the following criteria apply:

1. Adolescents and adults aged \geq 12 years.
2. Participants with a clinical diagnosis of non-segmental vitiligo with depigmented area including $\geq 0.5\%$ BSA on the face, ≥ 0.5 F-VASI, $\geq 3\%$ BSA on nonfacial areas, ≥ 3 T-VASI, and total body vitiligo area (facial and nonfacial) not exceeding 10% BSA.
3. Participants who agree to discontinue all agents used to treat vitiligo from screening through the final safety follow-up visit. Over-the-counter preparations deemed acceptable by the investigator and camouflage makeups are permitted.
4. Male and female participants must be willing to take appropriate contraceptive measures to avoid pregnancy or fathering a child for the duration of study participation with the exception of the following:
 - a. Females of non-childbearing potential (ie, or surgically sterile with a hysterectomy and/or bilateral oophorectomy OR postmenopausal, ≥ 12 months of amenorrhea without an alternative medical cause).
 - b. Prepubescent adolescents.

Note: Information about specific types of acceptable contraceptive measures and duration of contraceptive use are provided in [Appendix A](#).

5. For adult participant, ability to comprehend and willingness to sign an ICF; for adolescent participant, written informed consent of the parent(s) or legal guardian and written assent from the adolescent participant.

Note: Adolescents, who during the course of the study become legal adults, will be asked for their consent to continue the study, and in the event of lack thereof, will be discontinued from further participation.

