8.1.5. Demography and Medical History

8.1.5.1. Demographics and General Medical History

Demographic data and general medical history will be collected at screening by the investigator or qualified designee and will include year of birth/age, race, ethnicity, medical and surgical history, and current illnesses. Medical history will include relevant medical or surgical treatment within the last 2 years that are considered to be clinically significant by the investigator.

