8.2.6.5. Dermatology Life Quality Index

The DLQI is a simple, 10-question validated questionnaire to measure how much the skin problem has affected the participant over the previous 7 days ([Finlay and Khan 1994](#)). Participants age ≥ 16 years will answer the questionnaire with (1) very much, (2) a lot, (3) a little, or (4) not at all.

The questionnaire is analyzed under 6 headings as follows:

- Symptoms and feelings (Questions 1 and 2)
- Daily activities (Questions 3 and 4)
- Leisure (Questions 5 and 6)
- Work and school (Question 7)
- Personal relations (Questions 8 and 9)
- Treatment (Question 10)

CDLQI is the youth/children's version of the DLQI. For participants who are age ≥ 12 years to < 16 years at baseline, the CDLQI will be completed instead of the DLQI throughout their participation in the study. This questionnaire is self-explanatory and can be simply given to the participant who is asked to fill it in and who may ask the help of the parent or guardian. The questionnaire is analyzed under 6 headings as follows:

- Symptoms and feelings (Questions 1 and 2)
- Leisure (Questions 4, 5, and 6)
- School or holidays (Question 7)
- Personal relationships (Questions 3 and 8)
- Sleep (Question 9)
- Treatment (Question 10)

Full details will be provided in the Study Manual.

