2.6.3	F-BSA
2.6.4	T-BSA
2.6.5	VNS Score
2.6.6	F-PhGVA Score
2.6.7	T-PhGVA Score
2.6.8	F-PaGIC-V Score
2.6.9	T-PaGIC-V Score
2.6.10	Color-matching Questions
2.6.11	DLQI Score
2.6.12	CDLQI Score
2.6.13	TSQM Score
2.6.14	HADS
2.6.15	WHO-5
2.6.16	VitiQoL Score
2.6.17	Participants With F-VASI Assessments Not Done Due to COVID-19 Pandemic
Adverse Events	
2.7.1	Adverse Events
2.7.2	Adverse Events Leading to Study Drug Discontinuation
2.7.3	Serious Adverse Events
2.7.4	Treatment-Related Adverse Events

Listing No.	Title
2.7.5	Adverse Events With a Fatal Outcome
2.7.6	Adverse Events Leading to Interruption of Study Drug
2.7.8	Grade 3 or Higher Adverse Events
2.7.9	Application Site Reactions
Laboratory Data	
2.8.1.1	Clinical Laboratory Values – Hematology
2.8.1.2	Clinical Laboratory Values – Chemistry
2.8.1.3	Abnormal Clinical Laboratory Values – Hematology
2.8.1.4	Abnormal Clinical Laboratory Values – Chemistry
Vital Signs	
2.8.2.1	Vital Signs
2.8.2.2	Abnormal Vital Sign Values
2.8.2.3	Alert Vital Sign Values

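### Does SAP 8.4 need to state which age (at baseline or at the visit) selects the vital-sign limits for adolescents who have a birthday on study?

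*SAP*

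**What the plan says.** SAP 8.4 gives the limits in three tables: Table 5, "Criteria for Clinically Notable Vital Sign Abnormalities for 12 to 15 Years Old"; Table 6, "Criteria for Clinically Notable Vital Sign Abnormalities for 16 to 17 Years Old"; and Table 7, "Criteria for Clinically Notable Vital Sign Abnormalities for ≥ 18 Years Old". For the output it says: "The abnormal values for participants exhibiting clinically notable vital sign abnormalities will be listed along with their assigned treatment group". An alert value must lie outside the same limits and also show a change of more than 25%. SAP Appendix A carries these as Listing 2.8.2.2 ("Abnormal Vital Sign Values") and Listing 2.8.2.3 (alerts), next to the full vital-signs Listing 2.8.2.1.

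No sentence fixes the date at which age is taken. SAP 4.2 defines only BMI and prior/concomitant medication. SAP 6.1.1 names age and age group without a derivation. SAP 4.1.3 defines baseline for measurements.

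Protocol 8.1.5.1 says that the demographic data and history taken at screening "will include year of birth/age, race, ethnicity, medical and surgical history, and current illnesses". For the quality-of-life questionnaire, Protocol 8.2.6.5 does fix age: for those aged 12 to under 16 at baseline, "the CDLQI will be completed instead of the DLQI throughout their participation in the study".

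**The concern.** The limits differ sharply between bands, and adolescents grow older during a 52-week treatment course. The Protocol foresees this: the note to inclusion criterion 5 deals with "Adolescents, who during the course of the study become legal adults". It also settled the matching question for the CDLQI by holding to baseline age. Nothing similar is written for vital signs.

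A systolic reading of 125 mmHg is not notable under Table 5, is notable under Table 6, and is not notable under Table 7. With no stated rule, the same participant's reading could be listed or left out depending on the programmer. The Week 52 output is also produced after the sponsor is unblinded, when one would rather have such conventions already fixed.

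A second oddity adds to the unease. The systolic upper limit runs 131, 120, 155 mmHg across the three bands. It is the only one of the ten limits that reverses direction with age, and no source is cited.

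**Working it through.** The plan states no figure to reproduce, so the check has three parts: who is exposed, which readings are affected, and which outputs use them.

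**Who is exposed.** Inputs: about 300 randomized and at least 10% adolescents (SAP 3); 24 + 28 = 52 weeks of treatment (Protocol 4.2). Assumptions: birthdays uniform over the year, and ages 12 to 17 evenly spread.

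- Adolescent floor: 0.10 × 300 = 30.
- Aged 15 or 17 on Day 1: 30 × 2/6 = 10. If their share is 20% or 50%, 30 × 0.20 = 6 or 30 × 0.50 = 15.
- Birthday by Week 24: 168/365.25 = 0.46, so 10 × 0.46 = 4.6 participants.
- Birthday by Week 52: 364/365.25 = 0.997, so essentially all 10, if they all enter and complete the optional extension.

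**Which readings are affected.** Comparing Tables 5 to 7 limit by limit (low / high):

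| Parameter | 12–15 | 16–17 | ≥ 18 | Flag differs at 16th birthday | Flag differs at 18th birthday |
|---|---|---|---|---|---|
| Systolic (mmHg) | 110 / 131 | 90 / 120 | 85 / 155 | 90–109, 121–131 | 85–89, 121–155 |
| Diastolic (mmHg) | 64 / 83 | 50 / 85 | 40 / 100 | 50–63, 84–85 | 40–49, 86–100 |
| Pulse (bpm) | 60 / 100 | 45 / 100 | 45 / 100 | 45–59 | none |
| Temperature (°C) | 35.5 / 38.0 | 35.5 / 38.0 | 35.5 / 38.0 | none | none |
| Respiratory rate (/min) | 8 / 20 | 8 / 20 | 8 / 20 | none | none |

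A row changes only if a reading taken after the birthday falls in one of these intervals. A row in the alert listing also needs a change of more than 25%.

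**Which outputs use the limits.** The by-visit summaries in SAP 8.4 (Tables 3.4.1.X to 3.4.5.X in Appendix A) report values, not breaches of limits. Appendix A has no table counting notable values by arm. The limits therefore reach only Listings 2.8.2.2 and 2.8.2.3.

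**What a programmer would do.** Protocol Table 3 schedules demography at screening only, and Table 4 has no demography row. SAP 6.1.1 places age among baseline and demographic characteristics, and SAP 7.3.2 lists it with participant characteristics and baseline variables. If the database holds only year of birth or age in whole years, exact age at a visit cannot be derived. The variable at hand is age at screening.

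**The case for a change.** The strongest argument for a change is that it would cost almost nothing. One sentence in SAP 8.4 would remove the ambiguity, the Protocol's CDLQI rule shows that the sponsor knows the issue, and an obvious default is easy to write down. The word baseline alone would not be enough, because SAP 4.1.3 resets the safety baseline for vehicle participants who cross over. A 15-year-old on vehicle could be 16 at that second baseline.

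Much of this stands. The SAP gives no reference date, the listings can differ, and a rule naming screening or double-blind baseline age would be tidier. What does not stand is that the omission puts anything at risk. The sentence would most likely confirm what analysts would do anyway. The point about unblinding carries little weight for a listing with no planned comparison. SAP 8 places sample displays in a separate document, and Appendix A treats its list and shells as a guideline, so a derivation of this kind may properly sit in programming specifications.

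On the systolic limit in Table 6, a sequence that falls and then rises is a fair reason for the sponsor to look at its source. It is not evidence of an error, and the documents contain nothing against which to test it.

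**Conclusion.** This is a missing programming detail that analysts fill sensibly, and no change to the plan follows. Under either reading every test, estimate and by-visit vital-sign summary is the same, and all readings remain in Listing 2.8.2.1, so any reader can apply the other table.

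About 10 participants are exposed (6 to 15 over the assumed range of age shares), and only for readings inside the intervals tabulated above. That count rests on the 10% adolescent floor, an even spread of ages and full continuation to Week 52. More adolescents would raise it, and early discontinuation or declining the extension would lower it. The documents do not allow an estimate of how many listed rows would actually differ. The systolic sequence of 131, 120, 155 mmHg is at most a query to the sponsor about its source.

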9. PLANNED ANALYSES

No formal interim analysis is planned in this study.

The primary analysis will occur after the primary database lock, when all participants have completed the vehicle-controlled, double-blind treatment period. Sponsors will be unblinded, while investigators and participants will still be blinded to the study treatment after the primary database lock.

10. CHANGES AND MODIFICATIONS TO THE ANALYSIS PLAN

All versions of the SAP are listed in [Table 8](#).

Table 8: Statistical Analysis Plan Versions

SAP Version	Date
Original	09 MAR 2020

10.1. Changes to Protocol-Defined Analyses

- The FAS will be used to replace ITT in evaluation of the efficacy during DB period. The participants with only baseline but not any postbaseline assessments are excluded from the FAS. Those participants are not considered to be able to contribute to the efficacy analysis because of missing data in postbaseline visits.
- Multiple imputation will be used to replace the NRI to handle missing values in the analysis for primary and key secondary endpoints. Multiple imputation is able to provide unbiased estimates of the parameters under MAR.
- DLQI/CDLQI have been moved from exploratory endpoints to secondary endpoints.

10.2. Changes to the Statistical Analysis Plan

Not applicable.

APPENDIX A. PLANNED TABLES AND FIGURES

This appendix provides a list of the planned tables, figures, and listings for the clinical study report. Standard tables will follow the conventions in the Standard Safety Tables current version. Shells are provided for nonstandard tables. In-text tables are identical in structure and content as appendix tables, but follow a Rich Text Format.

The list of tables, figures, listings, and the shells are to be used as guideline. Modifications of the list or shells that do not otherwise affect the nature of the analysis will not warrant an amendment to the SAP.

Tables

Table No.	Title	Population
Demographics and Disposition		
1.1.1	Analysis Populations	All
1.1.2.1	Summary of Participant Disposition in Double-Blind Period	Safety/FAS
1.1.2.2	Summary of Participant Disposition in Treatment Extension Period	TE
1.1.3	Summary of Number of Participants Enrolled by Country and Site	Safety
1.1.4.1	Summary of Protocol Deviations in Double-Blind Period	Safety
1.1.4.2	Summary of Protocol Deviations in Treatment Extension Period	TE
1.2.1	Summary of Demographics and Baseline Characteristics	Safety/FAS
1.2.2	Summary of Demographics and Baseline Characteristics	TE
1.3	Summary of Baseline Disease Characteristics	Safety/FAS
1.4.1	Summary of Prior Therapy for Vitiligo	Safety
1.4.2	Summary of Prior Medications	Safety
1.4.3.1	Summary of Concomitant Medications in Double-Blind Period	Safety
1.4.3.2	Summary of Concomitant Medications in Treatment Extension Period	TE
1.5	Summary of General Medical History	Safety
1.6	Summary of Participants With Assessments Not Done Due to COVID-19 Pandemic	Safety
Efficacy		
F-VASI / T-VASI		
2.1.1	Summary and Analysis of Participants Achieving F-VASI75 During the Treatment Period	FAS
2.1.1.2	Summary and Analysis of Participants Achieving F-VASI75 During the Treatment Period	PP
2.1.1.3	Summary and Analysis of Participants Achieving F-VASI75 by Skin Type During the Treatment Period	FAS
2.1.1.4	Summary and Analysis of Participants Achieving F-VASI75 by Age Group During the Treatment Period	FAS
2.1.1.5	Summary and Analysis of Participants Achieving F-VASI75 by Region During the Treatment Period	FAS
2.1.1.6	Summary and Analysis of Participants Achieving F-VASI75 by Sex During the Treatment Period	FAS
2.1.1.7	Summary and Analysis of Participants Achieving F-VASI75 by Race During the Treatment Period	FAS
2.1.1.8	Summary and Analysis of Participants Achieving F-VASI75 at Week 24 by F-BSA	FAS

Table No.	Title	Population
2.1.1.9	Summary and Analysis of Participants Achieving F-VASI75 at Week 24 by Tipping Point Analysis	FAS
2.1.2	Summary and Analysis of Participants Achieving F-VASI25 During the Treatment Period	FAS
2.1.3	Summary and Analysis of Participants Achieving F-VASI50 During the Treatment Period	FAS
2.1.4	Summary and Analysis of Participants Achieving F-VASI90 During the Treatment Period	FAS
2.1.5	Summary and Analysis of F-VASI During the Treatment Period	FAS
2.2.1	Summary and Analysis of Participants Achieving T-VASI25 During the Treatment Period	FAS
2.2.2	Summary and Analysis of Participants Achieving T-VASI50 During the Treatment Period	FAS
2.2.3	Summary and Analysis of Participants Achieving T-VASI75 During the Treatment Period	FAS
2.2.4	Summary and Analysis of Participants Achieving T-VASI90 During the Treatment Period	FAS
2.2.5	Summary and Analysis of T-VASI During the Treatment Period	FAS
F-BSA/T-BSA		
2.3.1	Summary and Analysis of F-BSA During the Treatment Period	FAS
2.3.2	Summary and Analysis of T-BSA During the Treatment Period	FAS
VNS		
2.4.1	Summary and Analysis of Participants Achieving VNS Scores of 4 or 5 During the Treatment Period	FAS
2.4.2	Summary of Participants in Each Category of VNS Scores During the Treatment Period	FAS
F-PhGVA/T-PhGVA		
2.5.1	Summary and Analysis of Participants Achieving an F-PhGVA of Clear or Almost Clear During Treatment Period	FAS
2.5.2	Summary of Participants in Each Category of F-PhGVA Scores During Treatment Period	FAS
2.6.1	Summary and Analysis of Participants Achieving an T-PhGVA of Clear or Almost Clear During Treatment Period	FAS
2.6.2	Summary of Participants in Each Category of T-PhGVA Scores During Treatment Period	FAS
F-PaGIC-V/T-PaGIC-V		
2.7.1	Summary and Analysis of Participants Who Report F-PaGIC-V of Very Much Improved or Much Improved During Treatment Period	FAS
2.7.2	Summary of Participants in Each Category of F-PaGIC-V Scores During Treatment Period	FAS
2.8.1	Summary and Analysis of Participants Who Report T-PaGIC-V of Very Much Improved or Much Improved During Treatment Period	FAS
2.8.2	Summary of Participants in Each Category of T-PaGIC-V Scores During Treatment Period	FAS
All Other Efficacy Parameters		
2.9.1	Summary of Participants in Each Category of Color-Matching Question During the Treatment Period	FAS
2.9.2	Summary of DLQI During Treatment Period	FAS

Table No.	Title	Population
2.9.3	Summary of CDLQI During Treatment Period	FAS
2.9.4	Summary of WHO-5 During Treatment Period	FAS
2.9.5	Summary of TSQM During Treatment Period	FAS
2.9.6	Summary of VitiQoL During Treatment Period	FAS
2.9.7	Summary of HADS During Treatment Period	FAS
Exposure & Compliance		
3.1.1.1	Summary of Exposure in Double-Blind Period	Safety
3.1.1.2	Summary of Exposure in Treatment Extension Period	TE
3.1.1.3	Summary of Exposure in During Treatment Period	Safety
3.1.2.1	Summary of Study Drug Compliance in Double-Blind Period	Safety
3.1.2.2	Summary of Study Drug Compliance in Treatment Extension Period	TE
3.1.2.3	Summary of Study Drug Compliance in During Treatment Period	Safety
Adverse Events		
3.2.1.1.X	Overall Summary of Treatment-Emergent Adverse Events	Safety
3.2.1.1.Y	Overall Summary of Exposure-Adjusted Treatment-Emergent Adverse Events	Safety
3.2.2.1.X	Summary of Treatment-Emergent Adverse Events by MedDRA System Organ Class and Preferred Term	Safety
3.2.3.1.X	Summary of Treatment-Emergent Adverse Events by MedDRA Preferred Term in Decreasing Order of Frequency	Safety
3.2.3.1.1.X	Summary of Treatment-Emergent Adverse Events $\geq 1\%$ in Any Treatment Group by MedDRA Preferred Term in Decreasing Order of Frequency	Safety
3.2.3.1.2.X	Summary of Application Site Reactions by MedDRA Preferred Term in Decreasing Order of Frequency	Safety
3.2.3.1.Y	Summary of Treatment-Emergent Adverse Events With Vehicle Group by MedDRA Preferred Term in Decreasing Order of Frequency During the Treatment Period	Safety
3.2.3.1.1.Y	Summary of Treatment-Emergent Adverse Events $\geq 1\%$ in any Treatment Group With Vehicle Group by MedDRA Preferred Term in Decreasing Order of Frequency During the Treatment Period	Safety
3.2.3.1.2.Y	Summary of Application Site Reactions With Vehicle Group by MedDRA Preferred Term in Decreasing Order of Frequency During the Treatment Period	Safety
3.2.3.1.3.Y	Summary of Exposure-Adjusted Incidence Rates of Treatment-Emergent Adverse Events With Vehicle Group by MedDRA Preferred Terms in Decreasing Order of Frequency During the Treatment Period	Safety
3.2.3.1.4.Y	Summary of Exposure-Adjusted Incidence Rates of Treatment-Emergent Adverse Events $\geq 1\%$ in Any Treatment Group With Vehicle Group by MedDRA Preferred Term in Decreasing Order of Frequency During the Treatment Period	Safety
3.2.3.1.5.Y	Summary of Exposure-Adjusted Incidence Rates of Application Site Reactions With Vehicle Group by MedDRA Preferred Term in Decreasing Order of Frequency During the Treatment Period	Safety
3.2.4.1.X	Summary of Grade 3 or Higher Treatment-Emergent Adverse Events by MedDRA System Organ Class and Preferred Term	Safety
3.2.4.2.X	Summary of Grade 3 or Higher Treatment-Emergent Adverse Events by MedDRA Preferred Term in Decreasing Order of Frequency	Safety
3.2.5.1.X	Summary of Serious Treatment-Emergent Adverse Events by MedDRA System Organ Class and Preferred Term	Safety
3.2.5.2.X	Summary of Serious Treatment-Emergent Adverse Events by MedDRA Preferred Term in Decreasing Order of Frequency	Safety

Table No.	Title	Population
3.2.6.1.X	Summary of Treatment-Related Treatment-Emergent Adverse Events by MedDRA System Organ Class and Preferred Term	Safety
3.2.6.2.X	Summary of Treatment-Related Treatment-Emergent Adverse Events by MedDRA Preferred Term in Decreasing Order of Frequency	Safety
3.2.7.1.X	Summary of Grade 3 or Higher Treatment-Related Treatment-Emergent Adverse Events by MedDRA System Organ Class and Preferred Term	Safety
3.2.8.1.X	Summary of Treatment-Related Serious Treatment-Emergent Adverse Events by MedDRA System Organ Class and Preferred Term	Safety
3.2.9.1.X	Summary of Treatment-Emergent Adverse Events With a Fatal Outcome by MedDRA System Organ Class and Preferred Term	Safety
3.2.10.1.X	Summary of Treatment-Emergent Adverse Events Leading to Dose Interruption by MedDRA System Organ Class and Preferred Term	Safety
3.2.11.1.X	Summary of Treatment-Emergent Adverse Events Leading to Discontinuation of Study Drug by MedDRA System Organ Class and Preferred Term	Safety
Laboratory Values and Vital Signs		
3.3.1.X	Summary of Laboratory Values – Hematology	Safety
3.3.3.X	Shift Summary of Hematology Laboratory Values in CTC Grade – To the Worst Abnormal Value	Safety
3.3.4.X	Summary of Laboratory Values – Chemistry	Safety
3.3.6.X	Shift Summary of Chemistry Laboratory Values in CTC Grade – To the Worst Abnormal Value	Safety
3.4.1.X	Summary of Systolic Blood Pressure	Safety
3.4.2.X	Summary of Diastolic Blood Pressure	Safety
3.4.3.X	Summary of Pulse	Safety
3.4.4.X	Summary of Respiration Rate	Safety
3.4.5.X	Summary of Body Temperature	Safety

Note: For AE tables ending with "X", separate tables will be provided for the double-blind period, treatment extension period, and the treatment period (double-blind and treatment extension periods).

Note: For AE tables ending with "Y", tables will be provided for the treatment period (double-blind and treatment extension periods). For participants who cross over, he/she should be included in both treatment groups.

Note: For Laboratory Values/Vital Sign tables ending with "X", separate tables will be provided for the double-blind period and treatment extension period.

Figure

Figure No.	Title	Population
4.1.1	Proportion of Participants Achieving F-VASI75 During Treatment Period	FAS
4.1.2	Proportion of Participants Achieving F-VASI25 During Treatment Period	FAS
4.1.3	Proportion of Participants Achieving F-VASI50 During Treatment Period	FAS
4.1.4	Proportion of Participants Achieving F-VASI90 During Treatment Period	FAS
4.1.6	Mean and Standard Error Plot of F-VASI During Treatment Period	FAS
4.1.7	Mean and Standard Error Plot of Change From Baseline in F-VASI During Treatment Period	FAS
4.1.8	Mean and Standard Error Plot of Percent Change From Baseline in F-VASI During Treatment Period	FAS
4.1.9	Forest Plot of Response Rate Difference in Achieving F-VASI75 at Week 24	FAS
4.2.1	Proportion of Participants Achieving T-VASI75 During Treatment Period	FAS
4.2.2	Proportion of Participants Achieving T-VASI25 During Treatment Period	FAS

Figure No.	Title	Population
4.2.3	Proportion of Participants Achieving T-VASI50 During Treatment Period	FAS
4.2.4	Proportion of Participants Achieving T-VASI90 During Treatment Period	FAS
4.2.6	Mean and Standard Error Plot of T-VASI During Treatment Period	FAS
4.2.7	Mean and Standard Error Plot of Change From Baseline in T-VASI During Treatment Period	FAS
4.2.8	Mean and Standard Error Plot of Percent Change From Baseline in T-VASI During Treatment Period	FAS
4.3.1	Mean and Standard Error Plot of F-BSA During Treatment Period	FAS
4.3.2	Mean and Standard Error Plot of Change From Baseline in F-BSA During Treatment Period	FAS
4.3.3	Mean and Standard Error Plot of Percent Change From Baseline in F-BSA During Treatment Period	FAS
4.4.1	Mean and Standard Error Plot of T-BSA During Treatment Period	FAS
4.4.2	Mean and Standard Error Plot of Change From Baseline in T-BSA During Treatment Period	FAS
4.4.3	Mean and Standard Error Plot of Percent Change From Baseline in T-BSA During Treatment Period	FAS
4.5	Proportion of Participants Achieving VNS scores of 4 or 5 During the Treatment Period	FAS
4.6	Proportion of Participants Achieving an F PhGVA of Clear or Almost Clear During Treatment Period	FAS
4.7	Proportion of Participants Achieving an T-PhGVA of Clear or Almost Clear During Treatment Period	FAS
4.8	Proportion of Participants who Report F PaGIC V of Very Much Improved or Much Improved During Treatment Period	FAS
4.9	Proportion of Participants who Report T-PaGIC-V of Very Much Improved or Much Improved During Treatment Period	FAS
4.10.1	Mean and Standard Error Plot of DLQI During Treatment Period	FAS
4.10.2	Mean and Standard Error Plot of Change From Baseline in DLQI During Treatment Period	FAS
4.10.3	Mean and Standard Error Plot of Percent Change From Baseline in DLQI During Treatment Period	FAS
4.11.1	Mean and Standard Error Plot of CDLQI During Treatment Period	FAS
4.11.2	Mean and Standard Error Plot of Change From Baseline in CDLQI During Treatment Period	FAS
4.11.3	Mean and Standard Error Plot of Percent Change From Baseline in CDLQI During Treatment Period	FAS
4.12.1	Mean and Standard Error Plot of WHO-5 During Treatment Period	FAS
4.12.2	Mean and Standard Error Plot of Change From Baseline in WHO-5 During Treatment Period	FAS
4.12.3	Mean and Standard Error Plot of Percent Change From Baseline in WHO-5 During Treatment Period	FAS
4.13.1	Mean and Standard Error Plot of TSQM During Treatment Period	FAS
4.14.1	Mean and Standard Error Plot of VitiQoL During Treatment Period	FAS
4.14.2	Mean and Standard Error Plot of Change From Baseline in VitiQoL During Treatment Period	FAS
4.14.3	Mean and Standard Error Plot of Percent Change From Baseline in VitiQoL During Treatment Period	FAS

Figure No.	Title	Population
4.15.1	Mean and Standard Error Plot of HADS During Treatment Period	FAS
4.15.2	Mean and Standard Error Plot of Change From Baseline in HADS During Treatment Period	FAS
4.15.3	Mean and Standard Error Plot of Percent Change From Baseline in HADS During Treatment Period	FAS

Listings

Listing No.	Title
Demographic and Baseline Characteristics	
2.1.1	Participant Enrollment and Disposition Status
2.1.2	Participant Inclusion and Exclusion Criteria Violations
2.1.3	Participants Who Discontinued Treatment or Discontinued From Study Due to COVID-19
2.1.4	Participants With Assessments Not Done Due to COVID-19 Pandemic
2.2.1	Protocol Deviations and Violations
2.3	Analysis Populations
2.4.1	Demographic Characteristics
2.4.2	Baseline Disease Characteristics
2.4.3	Medical History
2.4.4	Prior and Concomitant Medications
2.4.5	Prior Medications for Vitiligo
2.5.1	Study Drug Exposure and Compliance
Efficacy	
2.6.1	F-VASI Score
2.6.2	T-VASI Score
2.6.3	F-BSA
2.6.4	T-BSA
2.6.5	VNS Score
2.6.6	F-PhGVA Score
2.6.7	T-PhGVA Score
2.6.8	F-PaGIC-V Score
2.6.9	T-PaGIC-V Score
2.6.10	Color-matching Questions
2.6.11	DLQI Score
2.6.12	CDLQI Score
2.6.13	TSQM Score
2.6.14	HADS
2.6.15	WHO-5
2.6.16	VitiQoL Score
2.6.17	Participants With F-VASI Assessments Not Done Due to COVID-19 Pandemic
Adverse Events	
2.7.1	Adverse Events
2.7.2	Adverse Events Leading to Study Drug Discontinuation
2.7.3	Serious Adverse Events
2.7.4	Treatment-Related Adverse Events

Listing No.	Title
2.7.5	Adverse Events With a Fatal Outcome
2.7.6	Adverse Events Leading to Interruption of Study Drug
2.7.8	Grade 3 or Higher Adverse Events
2.7.9	Application Site Reactions
Laboratory Data	
2.8.1.1	Clinical Laboratory Values – Hematology
2.8.1.2	Clinical Laboratory Values – Chemistry
2.8.1.3	Abnormal Clinical Laboratory Values – Hematology
2.8.1.4	Abnormal Clinical Laboratory Values – Chemistry
Vital Signs	
2.8.2.1	Vital Signs
2.8.2.2	Abnormal Vital Sign Values
2.8.2.3	Alert Vital Sign Values
